### **Study Overview and Hypotheses**

We propose to screen patients with bipolar depression I or II, who are already on acceptable mood stabilization. They may or may not be on antidepressants at the time of screening but subjects on antidepressants would be taken off them before completing the screening phase. Those patients who have a depression of at least moderate severity without significant symptoms of activation or mania will be started on a course of open label TMS treatment of up to 35 sessions. Safety and efficacy assessments will be done weekly. Patients will complete a course of treatment when they meet remission criteria (MADRS score < 10) or at the end of 30 treatments, whichever comes first. Patients who are still judged to be improving between treatment 25 and treatment 30 will be eligible to complete up to five additional treatments as the discretion of each site's principal investigator.

Patients who meet response criteria (MADRS score decreases by at least 50%) will complete the full course of 30 to 35 TMS sessions. Patients will be withdrawn for safety concerns, particularly the onset of activation suggestive of mania or a mixed state.

Patients who meet response or remission criteria will be followed monthly for up to six months to evaluate the durability of response. They will be on standard mood stabilizing medications and psychotherapy per their clinician's discretion.

The primary study hypotheses are:

1. TMS will provide effective antidepressant treatment in patients with bipolar depression both type I and II.
2. TMS will show a shorter time to response in bipolar depressed patients compared with the available data in unipolar depressed patients.
3. TMS can be safely given in bipolar depression without inducing a manic or mixed episode switch in patients who are receiving adequate concurrent mood stabilizing medication

The secondary hypothesis is:

1. The majority of treatment responders will show adequate durability of response with remitters showing better durability.

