### Phase III: Six Month Follow Up

Patients' meeting response or remission criteria will be followed monthly for up to six months by in-person visits or phone interviews. The MADRS, CGI-S and CGI-I scales will be administered at each encounter. Relapse will be defined as a MADRS score of 20 or above for two consecutive weeks. Patients who meet relapse criteria will have an early termination visit the following week and referred for standard clinical treatment.

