### **Patient Withdrawal**

Patients will be told verbally and in the informed consent that they have the right to withdraw from the study at any time without prejudice or loss of benefits to which they are otherwise entitled.

The investigator may discontinue a patient from the study for the following reasons:

- Non-compliance with 5-day TMS treatment schedule. Patients must complete at least 4 consecutive days of treatment per week.
- It is the judgment of the investigator that the patient may be at risk for suicide
- The patient has rated a “yes” to question 4 or question 5 on the C-SSRS “Since Last Visit” version
- Patient meets relapse criteria (MADRS score  $\geq$  20 for two consecutive weeks
- Onset of manic or mixed symptoms
- Pregnancy
- Intercurrent illness, adverse event or any other reason concerning the well-being of the patient.

Patients who voluntarily withdraw from the study or who are discontinued from the study will be asked to complete an early termination visit. The early termination visit will be done one week after study withdrawal. A MADRS and CGI will be performed by the investigator. Patients will be referred back to their treating psychiatrist for standard clinical care.

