### **Statistical Methods**

- Sample Size

We are looking to collect sufficient data to demonstrate the efficacy and safety of TMS in bipolar depression. As this is an open label trial we will aim to treat 30 patients to achieve a reasonable sample size.

- Primary Efficacy Analysis

The primary outcome measure will be the percentage of patients who respond or remit after 30 to 35 treatments. We will subdivide patients based on the diagnosis of either bipolar I or bipolar II to compare effectiveness between those groups.

The other primary outcome will be the percentage of patients who meet criteria for onset of manic symptoms based on the YMRS. The patients will also be separated based on their diagnostic category.

- Secondary Efficacy Analysis

We will also look at the HAM-D and CGI to see the percentage of patients meeting response criteria.

For the patients meeting remission criteria, we will calculate the number of treatments required to achieve remission. Patients who only meet response criteria will be treated for 30 to 35 sessions.

Responders and remitters will also be followed for six months after the final treatment to see the durability of response. Percentage of patients' meeting relapse criteria will be calculated.

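### Durability is a bare percentage relapsing, with no denominator, no rule for patients who leave follow-up early and no interval, so the same data can support or contradict the majority-durable hypothesis

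*Combined protocol and SAP*

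**What the plan says.** The secondary hypothesis (Study Overview and Hypotheses) has two parts: "The majority of treatment responders will show adequate durability of response with remitters showing better durability". The whole analysis offered for it is one sentence at the end of Secondary Efficacy Analysis, which says that the percentage of patients "meeting relapse criteria will be calculated".

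The length of follow-up is described in two ways. The overview and the Phase III section set an upper limit: patients "will be followed monthly for up to six months by in-person visits or phone interviews". The Statistical Methods section states a fixed period: "Responders and remitters will also be followed for six months after the final treatment to see the durability of response".

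Relapse is defined in the Phase III section: "Relapse will be defined as a MADRS score of 20 or above for two consecutive weeks". Under Patient Withdrawal, patients are told that "they have the right to withdraw from the study at any time without prejudice". The investigator may also discontinue a patient for manic or mixed symptoms, suicide risk, pregnancy or intercurrent illness, none of which is relapse under the definition. Leavers are asked for one further MADRS and CGI: "The early termination visit will be done one week after study withdrawal".

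The documents do not give a denominator for the relapse percentage, a way to enter a leaver into it, a time-to-relapse method, a confidence interval, a numerical meaning for adequate durability, or an analysis of remitters against other responders.

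**The concern.** A percentage relapsing over six months is well defined only if everyone is followed for six months or until relapse. Here some patients can be expected to leave before either. The single rating after withdrawal cannot by itself show relapse, which needs a raised score over two consecutive weeks. The analyst must therefore decide what a leaver is, and the plan leaves that choice until the data are in hand.

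The choice matters because the hypothesis turns on a majority, which is a 50% line. The two obvious denominators move the estimate in opposite directions, so the conclusion could depend on a decision made after seeing the results. The second half of the hypothesis, that remitters do better, has no planned analysis and could not be answered from the single percentage.

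**Working it through.** **Figures in the documents.** There is no planned relapse rate, drop-out rate or power for durability to reproduce. The retrospective response rate in the Background does reproduce: 26/34 = 76.5%. Applied to the 30 patients in the Sample Size paragraph, 0.765 × 30 = 22.9, or about 23 patients entering Phase III. With the second site's 20 patients added, it is about 38.

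**Assumptions.** Let R be the probability of relapse by six months if nobody left, and D the probability of leaving by six months if nobody relapsed. Both are assumed, and ranges are shown. Hazards are constant and independent, with six months as the time unit:

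- λ = −ln(1 − R) and μ = −ln(1 − D)
- completers without relapse: C = (1 − R)(1 − D)
- relapse over all entrants: A = λ/(λ + μ) × (1 − C)
- relapse over relapsers plus completers: B = A/(A + C)

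**One case in full: R = 55%, D = 30%.** λ = 0.799 and μ = 0.357. C = 0.45 × 0.70 = 0.315. A = 0.799/(0.799 + 0.357) × 0.685 = 0.4735. B = 0.4735/(0.4735 + 0.315) = 0.6005. The share who leave before relapsing is 1 − 0.4735 − 0.315 = 0.2115, or about 5 of 23 patients. The true value of 55% becomes 47% or 60%.

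**Range.** Each cell gives A / B in percent.

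| True relapse R | D = 10% | D = 20% | D = 30% | D = 40% |
|---|---|---|---|---|
| 50% | 47.7 / 51.5 | 45.4 / 53.2 | 42.9 / 55.1 | 40.3 / 57.3 |
| 55% | 52.6 / 56.5 | 50.0 / 58.1 | 47.3 / 60.1 | 44.5 / 62.2 |
| 60% | 57.4 / 61.5 | 54.7 / 63.1 | 51.8 / 64.9 | 48.8 / 67.0 |
| 70% | 67.1 / 71.3 | 64.1 / 72.8 | 60.9 / 74.4 | 57.6 / 76.2 |

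Solving A = 50% gives the drop-out at which the all-entrants figure crosses the line: about 20% at R = 55%, 36% at 60%, 49% at 65% and 60% at 70%.

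**Sampling error.** With 23 responders and R = 55%, the binomial chance that 12 or more are recorded as not relapsed (all-entrants denominator) is 31% with no drop-out, 50% at D = 20% and 60% at D = 30%. The 31% comes from the small sample alone; the rise above it comes from drop-out. An observed 11/23 has an exact 95% CI of 27% to 69%.

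**Illustration with invented data.** Take 23 entrants, relapses of 2, 2, 2, 2, 1 and 1 in months 1 to 6, and two leavers after the relapses in each of months 1 to 3.

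- All entrants: 10/23 = 43.5% relapsed.
- Relapsers plus completers: 10/17 = 58.8%.
- Kaplan-Meier: relapse-free = 21/23 × 17/19 × 13/15 × 9/11 × 8/9 × 7/8 = 0.451, so 54.9% relapsed.
- All leavers counted as relapsed: 16/23 = 69.6%.

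**The case against.** The strongest reply is that this is a descriptive secondary result in a small open-label study with no test and no cut-off, so nothing is formally confirmed. Precision is also poor: an interval of 27% to 69% is far wider than a bias of about 8 points. Both statements are true. They argue for reporting an interval; they do not justify leaving the estimate undefined.

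A reader might infer that every drop-out biases the result towards durability, or that the plan counts leavers as durable. The documents do not support this. Counting over all entrants is the natural reading, but no denominator is named, and on relapsers plus completers the bias runs the other way.

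A reader might also infer that the hypothesis is likely to be wrongly supported. That is too strong. On the all-entrants denominator, reversal needs true relapse only modestly above 50% or heavy drop-out. At R = 60% and D = 30% the figure is still 51.8%.

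A third tempting inference is that remitters will be compared with a responder group that contains them, which would shrink the difference. The plan commits to no such comparison, and the Statistical Methods section already separates patients who meet only the response criterion. Nor is it certain that every remitter is a responder. The MADRS minimum of 20 applies at screening, which can last up to 28 days. If the baseline is a later score of, say, 17, a fall to 9 is 8/17 = 47%.

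Finally, the upper-limit wording for follow-up may only reflect that relapsers stop early, and some withdrawal reasons belong to the treatment phase. That is fair. The right to withdraw and the remaining non-relapse reasons are enough to make follow-up unequal.

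**Conclusion.** The concern holds as a gap in the estimator. The plan reduces durability to one percentage and does not say who is in the denominator, how early leavers count or how precise the result is. Under constant, independent hazards, with rates that are assumptions, a true relapse of 55% with 30% drop-out can be reported as about 47% or about 60%, on opposite sides of the majority line. The direction of bias is not known from the documents, and the further true relapse lies above 50%, the more drop-out it takes to reverse the answer on the all-entrants denominator. If leaving is linked to worsening mood, the all-entrants figure would understate relapse by more than shown here.

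The comparison of remitters with other responders is simply absent; no size of harm is claimed for it. Because the hypothesis is secondary, this is a change that should be made and not a threat to the main result.

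**What to change.** In Secondary Efficacy Analysis, replace the percentage with the following:

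- **Main estimate.** The Kaplan-Meier relapse-free proportion at six months after the last TMS session, with a 95% CI, for all who enter Phase III. Leavers are censored at their last MADRS.
- **Sensitivity analysis.** The same result counting every early leaver as relapsed. This is needed because Kaplan-Meier assumes that leaving is unrelated to prognosis, which is doubtful for withdrawal due to mania or suicide risk.
- **Leavers.** The number who left before relapse or six months.
- **Second half of the hypothesis.** The same estimate with CI, shown descriptively for two groups fixed at the end of Phase II: remitters, and patients who met only the response criterion. With about 23 responders in all, the comparison will be imprecise and should be described as such.

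The cost is a few lines of text. The monthly MADRS is already collected, so no visits, data or patients are added. The downside for the sponsor is that reported durability may look less favourable than a percentage over all entrants.

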### **Informed Consent, Institutional Review Board, DSMB, and Regulatory Considerations**

- Informed Consent

The investigator is responsible for ensuring that the patient understands the risks and benefits of participating in the study, including answering any questions the patient may have throughout the study and sharing any new information that may be relevant to the patient's willingness to continue his or her participation in the trial in a timely manner.

The informed consent document will be used to explain the risks and benefits of study participation to the patient in simple terms before the patient is entered into the study, and to document that the patient is satisfied with his or her understanding of the risks and benefits of participating in the study and desires to participate in the study.

The investigator is responsible for ensuring that informed consent is given by each patient (legal representatives will not be allowed for this trial). This includes obtaining the appropriate signatures and dates on the informed consent document prior to the performance of any protocol procedures and prior to the administration of study drug.

- Institutional Review Board (IRB)

The investigator will obtain documentation of IRB approval of the protocol and the informed consent. The IRB reviewing these documents is the Sheppard Pratt Institutional Review Board

The investigator will supply the IRB with:

1. Informed consent document.
2. Relevant curricula vitae
3. Patient recruitment materials and advertisements.

- Data Safety Monitoring Board

This committee will be composed of three psychiatrists experienced with the study population and qualified to serve in an advisory capacity in order to

evaluate safety and efficacy of the trial. The safety monitoring board will convene every six months or at other times if deemed necessary by the study investigator.

- Regulatory Considerations

This study will be conducted in accordance with the ethical principles that have their origin in the Declaration of Helsinki and that are consistent with good clinical practices and applicable laws and regulations.

The protocol will be submitted to [clinicaltrials.gov](http://clinicaltrials.gov)

## **Appendices**

Appendix 1: NeuroStar TMS Therapy® System Prescribing Information

Appendix 2: Analysis of Clinical Database on the Routine Clinical Care of Bipolar Depression with TMS

Appendix 3: Montgomery-Asberg Depression Rating Scale (MADRS)

Appendix 4: Mini International Neuropsychiatric Interview (M.I.N.I.) Version 6.0

Appendix 5: Young Mania Rating Scale (YMRS)

Appendix 6: Clinical Global Impression of Severity of Illness (CGI-S)

Appendix 7: Clinical Global Impression of Improvement (CGI-I)

Appendix 8: Columbia Suicide Severity Rating Scale (C-SSRS)

Appendix 9: 16-item Quick Inventory of Depressive Symptomatology – Self Report (IDS-SR 16)

Appendix 10: 17- item Hamilton Rating Scale for Depression (HAM-D17)

## **List of Tables**

Table 1 Study Schedule
